7.5.2.2 Secondary endpoints phase IIa

All summary statistics are provided by treatment arm.

7.5.2.2.1 AUC_{0-672h} (the area under the concentration-time curve of DZIF-10c in serum over the time interval from 0 to 672 hours (i.e. post drug administration until Day 29))

The same analyses will be performed as described in [Section 7.5.2.1.1](#).

This endpoint will be evaluated on the subject set PKS.

7.5.2.2.2 The frequency and magnitude of anti-drug antibodies targeting DZIF-10c

The same assessments will be performed as described in [Section 7.5.2.1.2](#).

This endpoint will be evaluated on the subject set TS.

7.5.2.2.3 SARS-CoV-2 RNA shedding in nasopharyngeal swabs determined by qRT-PCR in SARS-CoV-2-infected individuals

All evaluations for the first 7 days after drug administration will be done on the mITT set and will take data into consideration based on the time window around the corresponding visit as defined in [Section 6.7](#). The latest day to be taken into account is 7 days after drug administration. The evaluations for the later time points will be based on all subjects in the subject set TS who have at least a baseline value and a second measurement in the respective time period of viral RNA shedding in NP swabs by qRT-PCR.

Absolute viral load in SARS-CoV-2-infected individuals, as well as absolute and relative changes from baseline, will be summarised descriptively for each assessment time point and plotted by treatment arm and listed.

Time-weighted average change in viral load

The evaluation of viral load will be done by a time-weighted average change in \log_{10} viral load from baseline, defined by:

$$\frac{\sum_{i=a}^{b-1} \{0.5 * (Y_i + Y_{i+1}) * (t_{i+1} - t_i)\}}{(t_b - t_a)}$$

where

- Y_i = change from baseline in \log_{10} viral load at visit i
- t = time at the specified time point (the actual study day)
- a = baseline assessment at day 1
- b = last assessment at or prior to the threshold day (7 days after drug intake)

A parametric analysis of covariance (ANCOVA) model with corresponding baseline viral load and antibody status will be used. Adjusted means and 95% confidence intervals (CIs) will be provided. Missing values will not be imputed and since a linear trajectory on the log scale is expected, the normalisation by the denominator assures comparability of the values if t_b is different between patients.

Ratios between means (DZIF-10c vs placebo) will be calculated for each treatment arm separately for the respective time period. These calculations will be based on the mean time-weighted average change in viral load based on the ANCOVA model. CIs for the ratios will be reported for which the Delta method (Taylor method) will be used to calculate the variance of the ratios.

Mixed effect Model for Repeated Measures (MMRM)

In addition to a time-weighted average change, changes from baseline will also be evaluated using a restricted maximum likelihood (REML) based repeated measures approach. Analyses will include the fixed, categorical effects of antibody status, and treatment-by-visit interaction, as well as the continuous, fixed covariates of baseline and baseline-by-visit interaction. An unstructured (co)variance structure will be used to model the within-subject measurements. In

case the model does not converge, other covariance structures will be used sequentially until convergences is reached and the used covariance structure will be reported. The sequence of covariance structures to be used is as follows: unstructured, antedependence, heterogeneous Toeplitz, Toeplitz, heterogeneous AR(1). The Kenward-Roger approximation will be used to estimate denominator degrees of freedom.

All model-based evaluations (time-weighted average change and MMRM) will be done for the following time periods:

- first 7 days after drug administration
- first 14 days after drug administration
- first 28 days after drug administration

Note that only data points within the analysis periods are considered. Data available after the cut-offs will not be considered for the model based evaluations.

All model-based evaluation will be done for the SARS-CoV-2 E gene. As sensitivity analyses, the evaluations will be repeated for the additionally assessed SARS-CoV-2 gene (ORF1a/b gene). This sensitivity analysis will be done on subjects from the subject set TS who have at least a baseline value and a second measurement in the respective time period of viral RNA shedding in OP swabs by qRT-PCR.

Clearance rate

It will be shown how many patients fell below the limit of valid quantification. Finally, the proportions of participants with positive and negative PCR for each assessed SARS-CoV-2 gene assessed at every given visit will be described (clearance rate). Missing data will not be imputed. Consequently, the number of patients with non-missing data will be used as denominator for each proportion. CIs for the proportions will be derived as Clopper-Pearson intervals.

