#### **8.1.4. Secondary and Exploratory Outcomes and Target Variables**

Analysis is descriptive in nature. Secondary and exploratory endpoints will be evaluated by dose or treatment group and visit. Endpoints will be evaluated mainly in the safety population (dose escalation phase) or in the mITT population (**Group 2D**). Figures may show development over time where sensible. Endpoints can additionally be analysed by suitable multivariable models, including covariates. Substitution of missing values is not planned; the main efficacy analysis of time weighted average change of viral RNA shedding is possible in the mITT without substitutions. Complete methods will be specified in the SAP.

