6.3 SUBJECT SETS ANALYSED

- Screened set (SCS):
 - This subject set includes all subjects having signed informed consent and would correspond to the intention-to-treat set (ITT) in the phase I part of the trial.
- Randomised set (RS):
 - This subject set includes all randomised subjects in the phase IIa part of the trial, whether treated or not. This would correspond to the intention-to-treat set (ITT) in the phase IIa part of the trial
- Treated set (TS):
 - This subject set includes all subjects who received any amount of study drug.
- Modified Treated set (mTS):
 - This subject set includes all subjects who received any amount of study drug and did not require replacement in the phase I part of the trial. Details about requirement for replacement can be found below.
- Modified Intention-To-Treat set (mITT):
 - This subject set includes all randomised subjects in the phase IIa part of the trial that received any amount of study drug and who have at least a baseline value and a second measurement in the first week (up to 7 days after drug intake) of viral RNA shedding in nasopharyngeal swabs by qRT-PCR.

- PK parameter analysis set (PKS):
 - This subject set includes those subjects in the TS with at least one valid serum concentration of DZIF-10c available

Participants who are withdrawn from the trial after DZIF-10c administration will not be replaced, except for participants during the dose-escalation phase of the trial that are not followed until at least the day 7 visit after drug administration for reasons not related to safety events. Subjects who were replaced will be excluded from the primary analysis of the primary endpoint. Replacement of subjects will be determined on a case-by-case basis; exclusion of these subjects from the primary analysis will be confirmed by the trial team at the report planning meeting prior to database lock.

Please see [Table 6.3: 1](#) for a general overview which patient set will be used for which type of analyses. Additionally, biomarker analyses might be performed on subsets of the mITT set.

Table 6.3: 1 Subject sets used in the different types of analysis

Type of analysis	Subject set					
	SCS	RS	TS	mTS	mITT	PKS
Primary endpoints			X		X ^[1]	
Further endpoints				X		
Safety data, ADA & treatment exposure				X		
Demographic/baseline characteristics				X		
Disposition		X	X			
PK parameters						X
Viral Load				X ^{[1][2]}	X	

^[1] Will be used for the phase I part of the trial.

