6.7 BASELINE, TIME WINDOWS AND CALCULATED VISITS

As a general rule, the last assessment / measurement observed prior to start of trial medication will be assigned to baseline. Note that for some trial procedures (e.g., body weight, vital signs, laboratory tests) this may be the value measured on the same day trial medication was started. In these cases, it will be assumed that the measurements were taken prior to the intake of any study medication (if the measurement time was not captured). If no further data available, this can also be the last screening assessment. For viral load and pulmonary function test related

data it is paramount that the sample is taken prior to drug administration, and for these procedures time of sampling will be taken into consideration and compared to the time of drug intake.

Furthermore, for assessments of viral load data for the first 7 days after drug administration which require grouping to timepoints (e.g., descriptive statistics by timepoint, MMRM), the following will be done. Measurements for baseline (day 1) and days 2, 4, 6 and 8 will be included, where the measurement for day 6 is optional. The following time windows are allowed.

- The measurements for baseline and for day 2 must be taken exactly on the respective day. There is no time window.
- If there is no measurement on day 4, it will be replaced by a measurement on day 3 or day 5 with a preference for day 3.
- If there is no measurement on day 8, it will be replaced by a measurement on day 7.

If the optional measurement on day 6 is missing, it will be replaced by the value on day 5 or day 7 if these values have not been assigned to days 4 and 8, respectively. The measurement for day 5 will be preferred over day 7 if both values are available.

Additionally, for assessments of viral load data for the first 14 or 28 days after drug administration which require grouping to timepoints (e.g., MMRM), the following time windows apply. These analyses windows are non-overlapping and cover the whole trial period by using the middle between each scheduled visit.

- If there are no measurement on days 7 and 8, the day 8 measurement will be replaced by the earliest measurement up to day 11.
- If there is no measurement on day 15, it will be replaced by the closest measurement taken between day 12 and day 18.
- If there is no measurement on day 22, it will be replaced by the closest measurement taken between day 19 and day 25.

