9.2.1 Change from baseline

9.2.1.1 Time-weighted average change in viral load

Change from Baseline in Viral load:

```
#####
%MACRO auc (idvar =, dsname =, timevar =, yvar =, resultds =);
  %LOCAL lastid;
  %* All data manipulations are to be made outside of the macro;
  %* Sort dataset -> 1st data point is the starting point;
  PROC SORT DATA = &dsname OUT = _tmp;
    BY &idvar &timevar;
  RUN;

  %* Get last idvar;
  DATA _null_;
    y = COMPBL ("&idvar");
    y1 = COMPRESS (y);
    n = LENGTH (y) - LENGTH (y1);
    CALL SYMPUT ('lastid', COMPRESS (PUT (n+1, 5.)));
  RUN;

  %PUT lastid = &lastid;
  %LET lastvar = %SCAN (&idvar, &lastid, %STR ( ));

  DATA _tmp1;
    SET _tmp;
    RETAIN _ltime _lyvar _difftime _mintime;
    BY &idvar;
```

```

IF FIRST.&lastvar THEN DO;
  _ltime = &timevar;
  _lyvar = &yvar;
  _difftime = .;
  _mintime = &timevar;
END;
IF NOT FIRST.&lastvar THEN DO;
  auccomp = 0.5 * (&yvar + _lyvar) * (&timevar - _ltime);
  diff = (&yvar - _lyvar);
  difft = (&timevar - _ltime);
  _ltime = &timevar;
  _lyvar = &yvar;
  IF last.&lastvar THEN _difftime = &timevar - _mintime;
  OUTPUT;
END;
RUN;

PROC SUMMARY DATA = _tmp1;
BY &idvar;
VAR auccomp;
OUTPUT OUT = &resultds._pre SUM = auc;
RUN;

DATA &resultds;
MERGE &resultds._pre _tmp1 (WHERE = (_difftime NE .) KEEP = &idvar
_difftime);
BY &idvar;
auc = auc / _difftime;
RUN;
%MEND;

%auc (idvar = subject swab_type gene, dsname = rawdata3, timevar = day, yvar = log_cp_ml_d,
resultds = auc_result);
#####

```

9.2.1.2 Mixed effect Model for Repeated Measures (MMRM) of absolute change from baseline in viral load

Change from Baseline in Viral load via MMRM approach:

```
#####

```

```

ods exclude all;
ods output Diff0=diff0 classlevels=cl ConvergenceStatus=cs;
proc mixed data=viral_small_sim cl order=internal covtest;
  class usubjid trt01pn ady;
  model chg = antibs base base*ady trt01pn*ady / solution ddfm=Kenwardroger
  outpred=outpred1;
  repeated ady / type=un subject=usubjid;
  lsmeans trt01pn*ady / pdiff=control ("100" "&cutoffdays") obsmargins cl alpha=0.05
  slice=ady;
run;
ods exclude none;
#####

```

Where:

- usubjid = subject
- trt01pn = treatment arm (here numeric)
- ady = analysis day
- antibs = antibody status
- base = baseline viral load
- chg = change from baseline in viral load
- cutoffdays = day for analysis → 7 (primary analysis) or 28 (sensitivity analysis)

Note that the reference level in the code above (“100”) has to be adapted to the level used in the study.

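### Dividing by follow-up time does not make the time-weighted average viral-load change comparable across last-swab days; the planned ratio is exposed if those days differ by arm or depend on the rate of decline

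*SAP*

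**What the plan says.** SAP 7.5.2.2.3 takes Y as change from baseline in log10 viral load, sums it by trapezoids, and divides by t_b − t_a. The start point is "a = baseline assessment at day 1" and the end point is each participant's own: "b = last assessment at or prior to the threshold day (7 days after drug intake". Time is the actual study day. The macro in SAP 9.2.1.1 uses the same divisor ("auc = auc / _difftime"). The stated reason why different values of t_b do no harm is that "since a linear trajectory on the log scale is expected, the normalisation by the denominator assures comparability of the values".

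The resulting values enter an ANCOVA with baseline viral load and antibody status as covariates. The arms are then compared by the ratio of adjusted means, DZIF-10c to placebo, with Delta-method intervals. The model-based analyses cover 7, 14 and 28 days.

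The mITT set (SAP 6.3) requires only "at least a baseline value and a second measurement in the first week". Protocol 8.1.4 states that "the main efficacy analysis of time weighted average change of viral RNA shedding is possible in the mITT without substitutions". Protocol 8.1 plans no adjustment for dropouts in Group 2D.

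**The concern.** A change from baseline is zero at the start and, under the SAP's assumption, grows in proportion to time. Averaging it over a shorter period must give a smaller number, so dividing by the length of the period cannot make short and long follow-up comparable.

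Unequal t_b does not need dropout:

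- The SAP day-6 swab is optional (SAP 6.7: "Measurements for baseline (day 1) and days 2, 4, 6 and 8 will be included, where the measurement for day 6 is optional").
- Protocol Appendix II B allows the day-7 visit (SAP day 8) one day either side, and SAP Table 6.2: 1 lists two days either side. SAP 7.5.2.2.3 nevertheless uses nothing later than 7 days after dosing. A visit made a day late but within window therefore loses its swab, and t_b falls back to day 6, or to day 4 if the optional visit was skipped.
- The ANCOVA has no term for follow-up time.

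At stake is the TWA ratio, which is reported at interim analysis 2 (SAP 9.1.2) and is meant to inform later development.

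**Working it through.** The disputed statement is algebraic, and the plan gives no figure of its own to reproduce.

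**Formula.** Let s be the slope in log10 per day, T = t_b − t_a, and Y(t) = s(t − t_a). The trapezoid rule is exact for a straight line, so the area is sT²/2 and TWA = (sT²/2)/T = **sT/2**. One power of T remains. Division by T would equalise only a change that is constant over the whole interval, baseline included, and Y = 0 at baseline rules that out.

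**Individual values** (7-day analysis, SAP day labels, assumed s = −0.40):

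| Last swab | T | TWA | Share of day-8 value |
|---|---|---|---|
| Day 8 | 7 | −1.40 | 100% |
| Day 7 | 6 | −1.20 | 86% |
| Day 6 | 5 | −1.00 | 71% |
| Day 4 | 3 | −0.60 | 43% |
| Day 2 | 1 | −0.20 | 14% |

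The shares do not depend on s. In the 14- and 28-day analyses, still taking the trajectory as linear, a last swab on day 8 gives 3.5/7 = 50% and 3.5/14 = 25% of the full value.

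**Arm means.** If a share m of an arm lacks the day-8 swab, the mean is s × [(1 − m) × 3.5 + m × f], with f = 1.5 when day 4 is last and f = 2.5 when day 6 is last. Slopes and shares are assumptions.

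- *No drug effect (−0.40 in both arms), 10% missing on placebo, 30% on active.* Day 4 last: −0.40 × 3.3 = −1.32 and −0.40 × 2.9 = −1.16, ratio 0.88; with the shares swapped, 1.14. Day 6 last: −0.40 × 3.4 = −1.36 and −0.40 × 3.2 = −1.28, ratio 0.94; swapped, 1.06.
- *Slopes −0.40 placebo and −0.50 active (true ratio 1.25), same shares.* Day 4 last: −1.45/−1.32 = 1.10; swapped, −1.65/−1.16 = 1.42. Day 6 last: 1.18; swapped, 1.33.
- *Same slopes, 20% missing in both arms, day 4 last.* −1.55/−1.24 = 1.25, so the ratio is unchanged. The difference shrinks from −0.35 to −0.31.

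**Simulated ANCOVA** (20 per arm, no drug effect, day 4 last when day 8 is missing; assumed slope SD 0.15, residual SD 0.7; 1,500 runs). Nominal 5% rejection was 4.9% with nothing missing, 4.7% at 20%/20%, 7.3% at 10%/30% and 20.9% at 0%/40%. No formal test is planned, so these rates only show how far the intervals could mislead.

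**The case against.** A reader might infer that any missed late swab biases the antiviral comparison. The documents do not support that. The planned comparison is a ratio, and it is unaffected when t_b has the same distribution in both arms and is unrelated to decline, as the 20%/20% case shows.

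A reader might also infer that both documents rest on the linearity argument. Only the SAP makes it; Protocol 8.1.4 says merely that the analysis can be done without substitution. Nor can the shifted ratios be judged against the 1.45 in Protocol 8.2. That figure is an AUC ratio from simulations whose inputs and AUC definition are not given.

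Other points stand. The 10%/30% case means 2 against 6 of 20 participants and is only an illustration. Protocol 5.6 allows home visits during quarantine, which should limit missed swabs. The by-visit MMRM, which is also reported at interim analysis 2, does not use this normalisation, and SAP Table 6.2: 1 records first-week timing violations. Viral load is a secondary endpoint in an unpowered, hypothesis-generating trial. Setting unquantifiable values to a fixed level (SAP section 5) also breaks linearity, so the percentages above would not hold exactly.

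None of this rescues the sentence. The MMRM is additional to the TWA and does not repair the TWA ratio.

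**Conclusion.** Wrong as written, and it should be corrected. Under the SAP's own linear assumption the TWA is proportional to follow-up time. This part is exact and needs no assumed rates. Early t_b pulls each arm's mean, and the difference between arms, towards zero.

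Bias in the ratio is conditional: it arises, in either direction, only if t_b differs in distribution between arms or depends on the rate of decline. Its size cannot be determined because the documents give no missing-swab rates. The illustrated null ratios of 0.88 to 1.14 rest on the assumed 10%/30% imbalance. The matter merits correction because Protocol 8.1.4 treats the TWA as the main efficacy analysis and the SAP offers a false assurance in place of any handling of unequal follow-up.

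**What to change.** Delete the comparability sentence. Define the TWA over a fixed horizon and estimate it per arm from the planned MMRM as a trapezoid-weighted sum of visit means of change from baseline. In SAP day labels (day 1 is baseline, change zero):

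- 7 days: (1.5 × Day 2 + 2 × Day 4 + 2 × Day 6 + 1 × Day 8)/7
- 14 days: (1.5 × Day 2 + 2 × Day 4 + 2 × Day 6 + 4.5 × Day 8 + 3.5 × Day 15)/14
- 28 days: (1.5 × Day 2 + 2 × Day 4 + 2 × Day 6 + 4.5 × Day 8 + 10.5 × Day 15 + 7 × Day 29)/28

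Each weight is half the sum of the two adjacent intervals. For a straight line the three sums give 24.5/7 = 3.5, 98/14 = 7 and 392/28 = 14 times the slope, which is T/2 as required. Day 22 is left out because Protocol Appendix II B schedules no such visit for infected participants, although SAP 6.7 provides a window for it.

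Form the planned ratios and Delta-method intervals from these arm estimates and their covariance. Keep the per-subject ANCOVA on the mITT as supportive only; restricting it to participants with an end-of-period swab would introduce selection. Tabulate t_b by arm for each period.

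The cost is SAP wording, a little extra programming, and explicit reliance on the MMRM's missing-at-random assumption, including for the optional day-6 mean. No new data are needed.

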### **8.2. Sample Size Considerations**

During the dose escalation phase of the trial, a routine 3+3 trial design will be employed.

Since this is a hypothesis-generating trial, no formal sample size calculation is done for the randomized expansion study part. Selection of the group size included considerations of feasibility for an early phase first-in-human trial in quarantined individuals while facilitating outcome measures that can inform later stage trials. 60 participants will be included in the

expansion cohort with 20 participants per arm. Assuming a similar rate of participants experiencing Adverse Events as observed in a previous clinical trial of a SARS-CoV-2-neutralizing antibody in ambulatory SARS-CoV-2-infected participants, the following confidence intervals for the rate of Adverse Events in the expansion cohort can be calculated per group of 20 participants:

Rate of AEs (Participants)	90% confidence interval (Participants with AEs)
20%	[5% ; 35%]
25%	[9% ; 41%]
30%	[13% ; 47%]

While this exploratory trial is not powered to determine statistically significant differences in the change of the viral load between the treatment arms in the expansion cohort, simulations based on effects observed for previously reported SARS-CoV-2 neutralizing antibody responses indicate that an AUC ratio  $>1.45$  between a treatment arm of with a similar effects and controls can be observed with  $>80\%$  probability at a group size of 20.

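### The only between-arm contrast planned for the time-weighted viral-load change is a ratio with a Delta-method interval of unstated scale; read on the raw scale, that interval sits too low at 20 per arm

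*SAP*

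**What the plan says.** SAP 7.5.2.2.3 (phase IIa, nasopharyngeal swabs) defines the TWA change in log10 viral load and its model: "A parametric analysis of covariance (ANCOVA) model with corresponding baseline viral load and antibody status will be used". For the arm means, "Adjusted means and 95% confidence intervals (CIs) will be provided". The comparison between arms follows: "Ratios between means (DZIF-10c vs placebo) will be calculated for each treatment arm separately for the respective time period", and "CIs for the ratios will be reported for which the Delta method (Taylor method) will be used" to obtain the variance of each ratio.

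That section does not say whether the interval is formed on the ratio or the log-ratio scale, nor whether the covariance of the adjusted means enters the variance. It names no adjusted difference in TWA. The model is run for the first 7, 14 and 28 days.

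The MMRM in the same section is a separate analysis of change from baseline by visit. Its example code in SAP 9.2.1.2 requests differences from control ("lsmeans trt01pn*ady / pdiff=control") with 95% limits.

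Protocol 8.1.4 treats the TWA change as the main efficacy analysis, and SAP 9.1.2 includes it in interim analysis 2, which is to inform later development. Protocol 8.2 plans an "expansion cohort with 20 participants per arm" and says the trial is not powered for viral-load differences. SAP 7.5 rules out formal testing of secondary endpoints.

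**The concern.** Both adjusted means are expected to be negative, so a ratio above 1 favours DZIF-10c. With 20 participants per arm the denominator is itself a noisy mean, and the sampling distribution of the ratio is skewed to the right. An interval placed symmetrically around the estimate ignores that skew, so both of its limits tend to be too low.

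As nothing is formally tested, estimates and intervals are the evidence a reader will have for antiviral activity. An interval that sits too low makes a true benefit look weaker than the same data show as a difference. It also makes an inactive arm look worse than placebo too often. Two-sided coverage does not reveal this, because too many misses on one side are offset by too few on the other.

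**Working it through.** **The plan's own figure.** Protocol 8.2 reports simulations that "indicate that an AUC ratio" above 1.45 can be observed with more than 80% probability at 20 per arm. This cannot be reproduced, because neither the SD nor the simulated true effect is given.

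**Inputs.** From the documents: 20 per arm, three arms, ANCOVA with baseline viral load and antibody status, 95% limits for the arm means. Residual df = 60 − 3 − 2 = 55, so the t quantile is q = 2.004. Assumed: a 95% level for the ratio as well, equal variances, zero covariance between adjusted means, no dropout, and the placebo mean and SD. Write mP for the placebo mean, vP and vT for the variances of the two adjusted means, R for the ratio, and c = SE/|mP| for placebo. At n = 20, c = (SD/|mP|)/√20.

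**Formulas (zero covariance).**
- Raw Delta: R ± q·√(vT + R²vP)/|mP|. With equal variances: R ± q·c·√(1 + R²).
- Fieller, equal variances, g = q²c²: [R ± q·c·√(1 + R² − g)]/(1 − g).
- Difference divided by |mP|, equal variances: (R − 1) ± q·c·√2.

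**Direction.** Testing R = 1 with the raw Delta standard error and testing the difference give z values whose quotient is √(vT + vP)/√(vT + R²vP). For an observed ratio above 1 this is below 1 whatever the SD. With equal variances it is √2/√(1 + R²): 0.90 at R = 1.2, 0.80 at 1.45, 0.63 at 2.0. For a positive ratio below 1 it exceeds 1, so apparent harm is overstated.

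**Worked example, observed ratio 1.45, c = 0.15.**
- Raw Delta: 1.45 ± 2.004 × 0.15 × √3.1025 = 1.45 ± 0.53, i.e. 0.92 to 1.98.
- Fieller: g = 0.090; (1.45 ± 0.522)/0.910, i.e. 1.02 to 2.17.
- Difference/|mP|: 0.45 ± 0.43, i.e. 0.02 to 0.88.

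The same data exclude no effect by Fieller and by the difference, but not by raw Delta. At c = 0.10 the gap is smaller: raw Delta 1.10 to 1.80, Fieller 1.15 to 1.88.

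**Simulated chance of showing benefit, true ratio 1.8** (400,000 trials per row). Raw and log Delta must exclude 1; the difference must exclude 0, which is equivalent to Fieller excluding 1.

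| Placebo mean, SD (assumed) | c | Raw Delta | Log Delta | Adjusted difference |
|---|---|---|---|---|
| −1.5, 0.8 | 0.12 | 99% | 100% | 100% |
| −1.5, 1.0 | 0.15 | 88% | 96% | 96% |
| −1.0, 0.8 | 0.18 | 61% | 85% | 87% |
| −1.0, 1.0 | 0.22 | 18% | 64% | 70% |
| −0.5, 1.0 | 0.45 | 0% | 3% | 24% |

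At a true ratio of 1.45 with placebo −1.5 and SD 1.0, the figures are 30%, 52% and 56%.

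**Where the misses fall.** At placebo −1.0, SD 1.0, ratio 1.8, raw Delta coverage is 93.8%: 6.2% of intervals lie wholly below the truth and 0.0% wholly above. Coverage is 94.5% to 95.0% in the three rows above that one and 91.0% in the last. Fieller coverage is about 95% in every row.

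**No effect (true ratio 1.0).** The raw Delta interval lies wholly below 1 in 4.2% of trials (−1.5, SD 0.8), 4.8% (−1.0, SD 0.8) and 5.3% (−1.0, SD 1.0), against 2.5% nominal.

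**The case against.** The strongest reply is that the SAP fixes only how the variance is obtained. A log-scale Delta interval could be intended, and it would recover most of the loss: 64% against 70% in the fourth row, 85% against 87% in the third. This stands in part. The raw scale is an inference, though the natural one, because the text speaks of the variance of the ratio and not of its logarithm. Leaving the scale open is itself a gap, and the log scale does not help when the placebo decline is small (3% against 24%).

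Second, the size rests on assumed means and SDs. This stands. With a precise placebo mean the loss is negligible, and the last row is an extreme case: the placebo mean there is not distinguishable from zero in about 41% of simulated trials.

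Third, a reader might infer that the plan has no adjusted between-arm difference in viral load, or that real antiviral effects will be hidden. The documents do not support either. The MMRM code gives differences from placebo with confidence limits, and adjusted TWA means by arm are reported, so their difference can be computed, though without its own interval. The MMRM contrasts are visit-level, however, and do not supply an interval for the TWA difference.

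Fourth, the analysis is exploratory and unpowered, and no decision rule depends on whether the interval excludes 1. This limits the consequence. It does not justify an interval whose errors fall almost all on one side when a better one comes from the same model.

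**Conclusion.** The point holds as a weakness in how the main antiviral contrast is reported. If the Delta interval is formed on the ratio scale, it is shifted downward: the direction follows from algebra (zero covariance, observed ratio above 1), whatever the SD. The size is conditional. It ranges from about nothing (99% against 100%) to severe (18% against 70%) over plausible but assumed placebo values. With no effect, the interval signals harm in about 4–5% of trials instead of 2.5%.

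Two stronger readings should be avoided. The SAP does not state that the interval is symmetric; that is inferred. Nor can it be said that the analysis will hide an active drug: the loss depends on quantities the documents do not give, and the MMRM provides other adjusted contrasts. What can be said is that the TWA comparison may understate a benefit and that its interval is not fully specified.

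**What to change.** In SAP 7.5.2.2.3, for each analysis period, add the ANCOVA-adjusted difference in TWA change (each DZIF-10c arm minus placebo) with its 95% CI. If the ratio is kept, replace the Delta interval with Fieller's, computed from the covariance matrix of the adjusted means, and state the confidence level. Report the Fieller interval as it falls, including when it is unbounded, and add no rule for suppressing it: an unbounded interval tells the reader that the placebo change is too imprecise to serve as a denominator.

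The cost is a few sentences in the SAP, one extra estimate from a model already planned, and a short calculation for Fieller's limits. The drawback is that these limits may be wide or unbounded when the placebo change is near zero; the adjusted difference remains interpretable then.
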